Building on this work, and using a mixed-method approach incorporating qualitative and quantitative research, we propose to adapt the developed HWLs to young WP smokers in Florida and test them to answer an important policy question: Are pictorial HWLs on the WP device more effective than no-HWL (control) in increasing harm perception and intention to quit, and reducing smoking satisfaction, intensity, and exposure to toxicants? Accordingly, we will recruit young (18-29 yrs) WP users to:

1. Conduct 6-8 mixed-gender focus groups ($n \approx 65$) to adapt the 12 HWLs to our local population of young adults on risk communication, explore optimal HWLs placement and size, and select the top 4 HWLs for testing in Aim 2.
2. Conduct a clinical lab experiment among 248 WP smokers categorized according their use frequency (beginner vs. established smokers) to test the performance of the top 4 HWLs on the WP device compared to no-HWL (control) on harm perception, intention to quit, puffing behavior, dependence (e.g. satisfaction, withdrawal), and toxicant exposure (CO, nicotine, oxidative stress). Three months later, participants will receive a phone call to assess longer-term adaptations as a result of exposure to HWLs (e.g. quit intention, quitting).
3. Partner with *Golin, Tobacco-Free Workgroup, and Truth Initiative* to advocate for the adoption of HWLs policies and disseminate knowledge about WP harmful effects to young people in Florida and nationally.

Communicating WP risks through HWLs promises to reduce WP use and WP-related morbidity and mortality among young adults in Florida. This pioneering work will provide the first evidence-based WP HWLs to advance WP control in Florida, and a model for other states to respond to the WP epidemic.

Scientific Abstract: (2,083/2,100 characters)

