- 2. Test the top 4 HWLs in a clinical lab experiment.** Using the top 4 HWLs on the device, we will recruit 2 groups of WP smokers (n= 248; age 18-29 yrs) based on their use frequency (beginners, established) for a within- (HWL vs no-HWL; pre- vs post- smoking) and between-subject (beginner vs. established; 4 HWLs) experiment. Participants will be randomly assigned to one of the 4 HWLs conditions and undergo 2 smoking sessions that differ by HWL (HWL vs. no-HWL), with pre-post smoking assessment of harm perception, intention to quit, and toxicant exposure. Participants will receive a follow-up phone call 3-month after exposure to assess longer-term changes in quit attitude and behavior. *We hypothesize that applying pictorial HWLs to the WP device will; 1- significantly increase harm perception and intention to quit, and reduce puffing behavior, satisfaction, and exposure to toxicants compared to no-HWL; 2- this effect will be more pronounced in beginner than established smokers.*
- 3. Disseminate knowledge.** We will partner with *Golin, Tobacco-Free Workgroup, and Truth Initiative* to advocate for the adoption of HWLs policies and disseminate knowledge about WP harmful effects to young people in Florida and nationally.

Impact: Communicating WP risks through HWLs promises to reduce WP use and WP-related morbidity and mortality among young adults in the US.

Research Strategy (68,000 characters) 69,450

A. SIGNIFICANCE

This application is a resubmission. We thank the reviewers for their constructive comments and positive evaluation of our application. It was encouraging that the reviewers identified several strengths and the overall value of our proposal and gave it an “Outstanding” total impact score of “2”. We equally recognize our application shortcomings identified by the reviewers and tried our best to respond to them thoroughly in this resubmission. Our response letter provides a summary of changes made (pls. see response letter), while the revisions introduced in the proposal are marked by italics.

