C.2. Conceptual model: For the evaluation of HWLs, we adopted the message impact framework that is based on communication (McGuire 1981, Petty 2018) and health behavior theories (Fishbein 1975), and has been used applied successfully in cigarette HWL research (Noar 2016, a). This model assumes that features of the HWLs will influence behavior through a chain of psychological events including how HWLs will: 1- attract smokers, 2- influence emotion (e.g. attention, fear), 3- affects cognitive reaction such as thinking about the risk (harm perception), then 4- intention to change the behavior (intention to quit), and ultimately 5- change behavior (e.g., reduce or quit smoking) (Figure 7). Our mixed-method approach will allow us to measure these outcomes throughout our proposed research. For example, Aim 1 will allow us to assess communication outcomes mainly (e.g. attention, reaction), while Aim 2 will allow us to measure additionally subjective and objective outcomes such as perceived harm, intention to quit, smoking behavior, and exposures. Applying a robust theoretical model, will allow us to study the effects of HWLs on important policy and regulatory outcomes, and suggest plausible mechanisms of HWLs action to advance HWL research.

C.3. Considerations informing our approach:

C.3.1. Participants. We are targeting young people aged 18-29 yrs, since this age group is particularly vulnerable to WP uptake and progression (Barnett 2017, Kasza 2017, Florida Department of Health 2018). As some of our outcomes in the lab study are related to nicotine dependence, we will target 2 groups of WP smokers based on their use frequency; beginner, and established smokers. This adds to the complexity of studies, but considering common WP use patterns among our target population and the reviewers' comments, it seemed imperative to assess our outcomes in WP smokers at different stages of their smoking trajectory ([name] 2019, a). In addition, participants who participated in our previous research (e.g., pilot study) and those who will be recruited in the focus groups study will be excluded from the lab study to avoid contamination.

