Participants and recruitment. We will target young adults (age 18-29 years) in Florida who are regular WP smokers defined as smoking WP at least once a week in the past 6 months ([name] 2016); and are willing to provide informed consent and attend the focus group session as required. Individuals who report smoking cigarettes or other tobacco/nicotine products (e.g., e-cigarettes, pipes, cigars) will be included to increase the generalizability of results given that concurrent tobacco use is common among young WP smokers in the US (Primack 2013, Kasza 2017). We will recruit participants using a combination of online, offline and in-person recruitment methods to ensure successful recruitment (Buller et al., 2012). Offline items such as posters, flyers and study inserts will be posted and distributed on University of Miami and FIU campuses, nearby off-campus locations, and around WP cafés/bars in Miami. Online recruitment will include student listservs, Facebook, and other social media. In-person recruitment will involve handing out flyers and word-of-mouth targeting WP venues in Miami. Recruitment materials will be IRB approved and will have contact information (phone, e-mail) for initial eligibility screening. Interested callers will be screened by phone, and if eligible will be scheduled for a focus group session. *Each participant will be compensated \$36 at the end of the focus group session.*

Procedures. We will conduct 6-8 mixed-gender focus groups with regular WP smokers ($n \approx 65$; age 18-29 years). We plan to recruit equal numbers of women and men. Using a grounded theory approach aimed at generating, confirming and modifying theory (Strauss 1990), data will be examined iteratively and data collection will continue until saturation is reached, indicating that no new themes are emerging; i.e. the planned groups' number (6) is tentative. After the focus group discussion, participants will independently complete a brief survey to rate each HWL in term of self-perceived effectiveness. [name], a specialist in qualitative research will moderate the focus group and train a Research Assistant (RA) to help in conducting the focus groups. Open-ended questions and probes will be developed to guide the discussions and

ensure consistency across groups. The moderator guide and the brief survey will be developed by [name], [name] and [name] our public health designer.

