Design and Setting. Utilizing clinical lab methods, this aim provides broad testing of the top 4 HWLs on a myriad of WP smokers' subjective and objective outcomes. *We will recruit 2 groups of WP smokers (124 each, total 248; age 18-29 yrs) based on their use frequency (beginners: started WP smoking in the past 6 months, but smoke WP less than weekly; established: smoked at least once a week in the past 6 months) for a 2x2x2x4 within-subject (2: HWL vs no-HWL x 2: pre- vs post- smoking) and between-subject (2: beginner vs established smokers x 4: HWLs) experimental study. Participant in each group (beginner, established smoker) will be randomly assigned to one of the 4 HWLs conditions, and undergo 2 WP smoking sessions that differ by HWL on the WP device (HWL vs. no-HWL), with pre-/post-smoking assessment of harm perception, intention to quit, puffing behavior, satisfaction, urge to smoke, and toxicant exposure (CO, nicotine, oxidative stress) (Figure 9). We will use Latin Square crossover design balanced for carry-over effect (random order of 4 HWL condition), and to ensure equal distribution of study participants across gender. Accordingly, every subject will undergo 2 WP smoking sessions in the clinical lab setting differing by label (HWL vs. no-HWL) in a balanced random sequence; the same number of subjects gets each label and its order (1st or 2nd session) the same number of times, and for each gender. As in (Evans 2015, Brewer 2016, Brewer 2019), all participants will receive a follow-up phone call assessment after 3 months of the last session to evaluate the longer-term effect of exposure to the HWLs in real-world setting including HWLs recall, social interactions about WP harms (talk about HWLs with family/friends), and behavioral adaptations in response to exposure to HWLs (e.g., harm perception, quit intention, quitting).*

Such an approach allows:

- 1- Thorough comparisons without the need for large samples using powerful within-between subjects design.
- 2- Comparative testing for HWLs with current practice (no label control).
- 3- Comparative assessment of the 4 HWLs, and the themes they represent, on important

outcomes through between-subjects pre-post analysis.

4- Assessment of the expected effect of HWLs on WP smokers at different stages of their smoking trajectory.

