Inclusion Criteria. Participants need to be generally healthy (at a screening physical examination), between the ages of 21-35 years, willing to provide written informed consent, attend the lab as required, abstain from WP or any tobacco/nicotine for ≥ 12 h prior to study verified by expired air carbon monoxide eCO<5 ppm (Ben Taleb 2018), and use a WP to smoke tobacco in the lab according to study protocol. The 12 hour abstinence period is needed to clear plasma nicotine from prior-to-study smoking (6-8 h after cessation is needed to clear plasma nicotine) (Benowitz 2009) and ensure that all study measures are influenced mainly by study conditions. *Self-reported WP use will be used to define 2 groups of WP smokers (beginners, established), which mostly reflects smokers at different stages of their WP use trajectory ([name] 2016). These are consistent with common WP use patterns among young people in the US, and our previous lab studies with WP smokers, which will enhance recruitment and generalizability of our results (Primack 2013, Haider 2015).*

Exclusion Criteria. As is standard for clinical lab studies involving smoking, safety concerns require that individuals with self-reported history of chronic disease, psychiatric conditions, history of cardiovascular disease, low or high blood pressure (BP) (systolic BP>150 mm Hg, or diastolic BP>100 mm Hg), seizures, or regular use of prescription medications (other than vitamins or birth control) be excluded (Ben Taleb 2018). Women will be excluded if they are breast-feeding or test positive for pregnancy (by urinalysis) at screening. Individuals who fail the eCO test may be rescheduled at another date.

Sample Size. We built our calculation of the sample size for this study on eCO differences in our HWL pilot study (pls. see preliminary studies C.1.2. and Figure 6), which reported a small-

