to-medium effect size (Cohen's $f=0.19$) depending on HWL condition ([name] 2019, b). *This study will include 248 WP smokers (124 beginners; 124 established) randomized to 4 groups (62 each) along the 4 tested HWLs. Using repeated measures ANOVA F test with 2 within and 2 between factors, a total sample size of 240 participants will have at least 80% power to detect small-to-medium size effect (Cohen's $f=0.2$) or larger for $2 \times 2 \times 2 \times 4$ within-subject (H WL condition and time) and between-subject (smoking frequency and 4 different HWLs) effects, as well as their interactions at 0.05 level of significance, assuming sphericity and a moderate correlation (0.5) among repeated measures (Cohen 1988). The proposed sample size will provide sufficient power to detect small to medium effects expected based on our pilot data ([name] 2019, b). It is also feasible as we have not encountered any difficulty in recruiting a large number of WP smokers in our lab studies ([name] 2019, a).*

Screening, Informed Consent. Individuals who are identified as potentially eligible based on the phone screening will be asked to attend an onsite-screening, which will involve assessment of inclusion/exclusion criteria, physical examination, and urine pregnancy testing for women. Prior to screening, potential participants will undergo a review of the study and consent procedures to ensure that they understand the study, its risks/benefits, and their rights as research participants. Consented (written) individuals will then undergo a physical examination conducted by the research nurse, who will have access to an on-call Medical Monitor (physician) in case of concern or for consultation at any point of the study as it is the standard practice in our lab ([name] 2019, a, [name] 2019, b). The physical examination will include measuring BP, heart rate, temperature, pulse oximetry, and weight/height. Successfully consented/screened participants will be scheduled for their 1st session and asked to abstain from all tobacco use 12 hours prior to it.

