Experimental Methods. Participants will be randomly assigned to one of the 4 HWLs conditions and attend the lab for two, ~2-h sessions, separated by a 48-h washout period, and differ by HWL on the device (H WL vs. no-HWL control). Session order will be randomly counterbalanced to avoid order effects; counterbalancing also will allow us to study the effect of HWL on smoking behavior prospectively (i.e. between sessions difference is expected to be less when the HWL condition is tested first). They will also be balanced across the 4 HWLs (62 sessions for each HWL) to allow for equal numbers and robust comparisons of the 4 HWLs and their representative themes.

At the beginning of the 1st session, participants will provide demographic and personal information including age, socioeconomic status, race/ethnicity, and detailed tobacco use history, especially WP use. Then abstinence will be verified by eCO<5 ppm. Those who have eCO>5 ppm will be rescheduled. Those who are abstinent will get familiarized with the study procedures, measures, and they will be given time to adapt to the lab.

After adaptation, continuous measurement of physiological responses begins, and 10 ml of venous blood is sampled, and participants are asked to respond to subjective measures (pls. see below Outcome Measures). They will then begin a maximum 45 min WP smoking session (time recorded) using a device fitted with the pre-selected HWL or no-HWL according to condition. The HWL will be placed in a constant location/size on the device, which will be placed in front of participant seat (at vision level). For each participant, preferred brand/flavor of WP tobacco (verified at screening) will be used to neutralize the effect of nicotine/flavor on study outcomes. We will follow our tested lab protocol developed to study the WP (Ben Taleb 2018), where prior to each session, the lab staff will pack the WP head with 15 g of the participant's favorite tobacco preparation and cover it with perforated foil. Tobacco will be heated with quick-light charcoal disks (33 mm diameter; 6.2 g; Three Kings, Holland, or similar brand). Initially, a single charcoal disk will be used, and several (pre-weighed) ½ charcoal disks will be made available to the participants so they can add *ad libitum* (Cobb 2012). The timing of each

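### The lab trial's inclusion criterion sets ages 21-35, but the aims, target population and design of the same 248-person trial say 18-29

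*Combined protocol and SAP*

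**What the plan says.** Everything here comes from the combined protocol and SAP.

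- **C.5 Aim 2, Inclusion Criteria:** participants must be "between the ages of 21-35 years, willing to provide written informed consent". The same sentence requires them to attend the lab and smoke a waterpipe there, so it is about the lab trial.
- **C.5 Aim 2, Design and Setting:** the two groups of 124 are given as "total 248; age 18-29 yrs".
- **Specific Aims, Aim 2:** "we will recruit 2 groups of WP smokers (n= 248; age 18-29 yrs", again tied to the sample size.
- **General Audience Abstract:** "we will recruit young (18-29 yrs) WP users to" introduces a list whose second item is the 248-person lab experiment.
- **C.3.1 Participants:** "We are targeting young people aged 18-29 yrs, since this age group is particularly vulnerable to WP uptake and progression". The paragraph goes on to discuss the lab study's beginner and established groups.

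Three further passages bear on the consequences. Under Screening, Informed Consent in C.5, people who pass the phone screen are "asked to attend an onsite-screening, which will involve assessment of inclusion/exclusion criteria". Under Participants and recruitment in C.4.1, the focus groups that choose the labels are drawn from the same younger range: "We will target young adults (age 18-29 years) in Florida who are regular WP smokers". Under Experimental Methods in C.5, at the first session "participants will provide demographic and personal information including age".

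**The concern.** An eligibility criterion decides each screening. As the plan stands, a 19-year-old is eligible under Design and Setting and ineligible under the Inclusion Criteria, and for a 32-year-old it is the other way round. Whichever decision staff make, it departs from part of the plan.

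What is at stake is the enrolled population and the reach of the conclusions. The plan justifies 18-29 as the group of interest and draws its conclusions about young people in Florida. If the written criterion is followed, the trial leaves out the youngest part of that group and adds people beyond its upper limit. Section D allots 36 months to the lab study, so an uncorrected mismatch could run through the whole of recruitment.

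**Working it through.** **1. Is it the same study?** Yes. The 21-35 range stands in the only Inclusion Criteria section for Aim 2. The 18-29 range is attached directly to the figure of 248 in two places (Specific Aim 2, and Design and Setting). In two more it is attached to the target population from which the 248 are drawn (General Audience Abstract, C.3.1). The Scientific Abstract gives no numeric range.

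**2. Could it be a typing slip or a superseded line?** Both limits differ, so one mistyped digit does not explain it. The text is a clean running sentence, not a broken table, a redaction or an amendment log. Section A says that resubmission changes are in italics; the 18-29 in Design and Setting is italicised and the 21-35 is not. That hints at the history but does not show which range is meant to govern.

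**3. How far do the ranges differ?** Counting single years of age, inclusive:

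| Set | Ages | Count |
|---|---|---|
| Stated target | 18-29 | 29 − 18 + 1 = 12 |
| Written criterion | 21-35 | 35 − 21 + 1 = 15 |
| In both | 21-29 | 29 − 21 + 1 = 9 |
| Target only | 18-20 | 12 − 9 = 3 |
| Criterion only | 30-35 | 15 − 9 = 6 |

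- If the Inclusion Criteria govern, 3/12 = 25% of the target ages are excluded and 6/15 = 40% of the admitted ages lie outside the target.
- If staff applied both statements together, only 21-29 would remain: 9/12 = 75% of the target ages.

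These percentages describe ages, not participants. Converting them to a share of the 248 needs an age distribution, which the document does not give.

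**4. Does it reach the analysis?**

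- The sample-size paragraph uses Cohen's f = 0.2, a 0.05 significance level, a correlation of 0.5 among repeated measures and the four design factors. Age is not an input. The allocation 2 × 124 = 4 × 62 = 248 holds under either range.
- Each participant completes one session with an HWL and one without, so the age range does not bias the within-person contrast.

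**5. Does it reach other arguments in the plan?** Yes, in two places.

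- The C.5 recruitment case cites waterpipe smoking of up to 34% among Florida college students. Section A.1 describes the survey behind that figure as covering ages 18-23. The written criterion excludes 18, 19 and 20, which is 3 of those 6 ages.
- The labels under test are selected by an 18-29 group, so under 21-35 the selection and testing stages would cover different ages.

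**The case against.** The best case on the other side is that the harm is modest and the working rule is clear enough. On-site screening applies the inclusion and exclusion criteria, and only one section of Aim 2 carries that heading, so on an ordinary reading 21-35 would be used; the combined 21-29 reading is not suggested anywhere. The main comparison and the sample size are untouched, the Statistical Analysis section does not name age as a stratum or covariate, and age is recorded, so the enrolled range can be reported. The age-year percentages need not resemble any share of participants, because recruitment leans on two campuses and waterpipe venues. The focus groups and the lab sample already differ by design: the former are weekly smokers, while half the latter smoke less than weekly.

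Most of these points limit the finding without answering it. The percentages are no more than counts of ages. The mismatch with the label-selection stage is secondary, and nothing in the document shows that people aged 30-35 respond differently. But if 21-35 is the working rule, the trial then departs from the population stated in its own design, aims and rationale. A phone screen also comes before the on-site visit, and its age range is not stated. Recording age allows description afterwards; it cannot bring back people turned away or undo enrolments.

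**Conclusion.** The contradiction is real and is not resolved anywhere in the document. Ages 18-20 and 30-35 are each eligible under one statement and ineligible under another; only 21-29 satisfies both. The effect is on enrolment and on the population the results describe, not on the validity of the within-person comparison or on the sample-size calculation. How many of the 248 would be affected cannot be derived. The conclusion rests only on the text and needs no assumption about how response varies with age. Because this is an operative eligibility rule, it should be settled before anyone is screened.

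**What to change.** State one age range and use it throughout. The document does not show which is intended, so the choice is the sponsor's.

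- **If 18-29 is intended:** amend the age limits in the C.5 Inclusion Criteria, a one-line change.
- **If 21-35 is intended:** amend the General Audience Abstract, Specific Aim 2, C.3.1 (including its justification for 18-29) and Design and Setting. Reword the conclusions about youth and young people to fit, revisit the recruitment argument built on students aged 18-23, and state that the labels were selected by an 18-29 group.

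Either way, the phone and on-site screening forms and the recruitment materials must carry the same range. The cost is editorial: negligible for the first option, and a handful of text changes for the second. The sample size and analysis model need no change.

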charcoal application will be noted as in (Shihadeh 2005a). Also for standardization, only one type of WP device will be used. Participants will inhale *ad libitum* and at the end of the smoking period 10 ml of blood will be sampled again, eCO will be measured, and subjective dependence measures (WP satisfaction, urge to smoke, withdrawal) will be assessed as in (Ben Taleb 2018). The session will terminate 30 minutes after the last puff, and the 2nd session will be scheduled. Although it is difficult for a clinical lab environment to perfectly imitate the typical WP social setting (e.g. WP café), we will try our best to make the session area relaxing and entertaining to facilitate natural smoking behavior (e.g., access to fresh magazines, and background music). The same procedure will be conducted in the 2nd session.

Outcome Measures. Outcome measures for this study and the timing of their measurement have been adopted based on our conceptual framework (Noar 2016, a) (Figure 7); their suitability for our study's objectives (Hanson 2009); being validated in studies of health communication and HWLs (Noar 2016, a); and their validated use in clinical lab studies of WP smokers (Ben Taleb 2019, [name] 2019, a, [name] 2019, b). These measures are described below (Table 1 & Survey Instrument, Section 2, Lab Study).

1. Harm perception will be asked pre-/post-smoking *and at 3-month assessment* using 1 item “To what extent are you thinking about the serious health effects of WP smoking?” (Thrasher 2012).
2. Intention and motivation to quit will be asked pre-/post-smoking *and at 3-month assessment* using 3 items; “Do you intend to reduce WP smoking?”, “Do you intend to quit WP smoking?”, and “How motivated are you to quit WP smoking in the next month?” (Carpenter 2004).
3. Recall will be asked at 3-month assessment using 1 item “*Try to recall what the HWLs warning information were stated and type it in the box below*”(Kees 2010).
4. Social interaction will be asked at 3-month assessment using 1 item “*Since you started the study, how many times did you have a conversations with your family/friends about the HWLs?*” (Brewer 2016).

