Statistical Analysis. Prior to analysis, physiological data will be averaged to produce a single baseline value for each measure (10 minutes prior to WP use) and for each 10- minute that a participant was actually using the WP. Topography data will be processed automatically by the topography instrument software to eliminate closely spaced puffs (i.e., IPIs < 300 msec). Such puffs are assumed to be part of the previous puff and the recorded volume and duration values will be added to that preceding puff ([name] 2009). After this procedure, any puffs less than 5 ml will be considered an artifact and automatically discarded. Remaining data will be averaged for each participant in each condition using all remaining values for puff volume, duration, number, and IPI (Shihadeh 2004). We will address the issue of stability of WP puff topography by correlating topography values across sessions (Shihadeh 2005a). For plasma nicotine, values below the limit of quantitation (LOQ) will be replaced with the value of the LOQ ([name] 2011). Demographical data will be examined to determine if there are significant between-group differences on measures that may be related to study outcome (some differences are expected due to design such as past 30-day WP use) though these are expected to be minimized as a virtue of randomization. Unexpected between-group differences will be considered as potential adjustment covariates in the primary analysis (Evans 2006). *The primary analysis of each outcome will involve a 4-factor analysis of variance (or covariance) with two within-subject factors; HWL (HWL vs. no-HWL/control) and time (pre-post smoking), and two between-subject factors; smoking frequency (beginner vs. established WP smokers) and HWL (4 group assignment). This approach will be extended into mixed-effects linear regression model in order to adjust for potential confounders such as gender, education, race, SES, and self-efficacy. To assess if gender has any effect on the results, it will be considered as a covariate and we will test the pre-planned interaction with it to determine heterogeneity of HWL by gender as well as potential differential effects.* We will test for carry over effect statistically and will control for it when testing for the primary factors (Senn 2002). Significance levels will be adjusted for violations of the sphericity assumption using Huynh-Feldt corrections (Keppel 1991). The mean square error terms for the overall interaction will be used to conduct Tukey's honestly significant difference test (Keppel 1991), with comparisons at $P < 0.05$ considered significant.

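### Comparing the between-session difference by session order does not isolate a persisting label effect: with two sessions it equals twice the session change minus persistence

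*Combined protocol and SAP*

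**What the plan says.** Under C.5 Aim 2, Design and Setting, "every subject will undergo 2 WP smoking sessions in the clinical lab setting differing by label (HWL vs. no-HWL) in a balanced random sequence". There are thus two sessions and two orders, and no participant repeats a condition. The same section states: "We will use Latin Square crossover design balanced for carry-over effect".

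Experimental Methods adds that the sessions are "separated by a 48-h washout period" and gives the purpose of the ordering: "Session order will be randomly counterbalanced to avoid order effects". It then gives the ordering a second use, "counterbalancing also will allow us to study the effect of HWL on smoking behavior prospectively", and explains in parentheses how this would show: the "between sessions difference is expected to be less when the HWL condition is tested first".

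Under Statistical Analysis, the primary model has "two within-subject factors; HWL (HWL vs. no-HWL/control) and time (pre-post smoking"), plus smoking frequency and label group between subjects. It has no session or order term. The section promises that carry-over will be tested and controlled for when the primary factors are tested, but names no contrast and does not tie that test to the prospective reading.

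**The concern.** The remark takes a smaller between-session difference in the HWL-first order as a sign that the label's effect lasts into the later unlabelled session. Any ordinary change between the first and second session produces the same pattern, or masks it. Such a change is plausible. Session 1 is the first time a participant smokes in the lab, the hose carries a pressure transducer, and beginners, who by definition smoke less than weekly, smoke again after 48 hours.

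Balancing the orders removes a session change from the average label effect. In a comparison between the orders it does the opposite and doubles the change. If participants smoke less in session 2 for reasons unrelated to the label, the remark's logic reads that as persistence. If they smoke more as they get used to the setting, real persistence is cancelled or reversed. Whether label effects last is a question that section C.7 itself calls important and seldom addressed.

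**Working it through.** **Inputs from the documents.** 248 participants in balanced orders (124 per order is implied by 248/2, not stated); correlation 0.5 among repeated measures and alpha 0.05 (Sample Size); pilot post-session eCO of 24.5 ppm without and 17.8 ppm with the label, a difference of 6.7 ppm (C.1.2); pilot Cohen's f = 0.19 (Sample Size).

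**Assumptions.** An additive model. The documents give no value for d and no SD for eCO. Reading f = 0.19 as (6.7/2)/SD gives SD = 3.35/0.19 = 17.6 ppm; a range of 10 to 25 ppm is shown.

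**The plan's own figure.** No figure is stated for the order contrast. The nearest is at least 80% power at N = 240 for f = 0.2. For the strictest between-subject test (8 cells, 7 df, 4 measurements), the noncentrality is 240 × 0.04 × 4/(1 + 3 × 0.5) = 15.36 and power is 81.8%, so the figure is reproduced on that reading. It does not bear on the order contrast.

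**Cell means.** Let μ be the unlabelled session-1 mean, t the label's reduction, d the change from session 1 to session 2 for any reason, and c the reduction carried into a later unlabelled session.
- HWL first: session 1 = μ − t; session 2 = μ + d − c. No-label minus label = t + d − c.
- No-HWL first: session 1 = μ; session 2 = μ + d − t. No-label minus label = t − d.
- Gap between orders (HWL-first minus no-HWL-first): (t + d − c) − (t − d) = **2d − c**.
- Average of the two orders: t − c/2, so d cancels from the label effect.
- Session totals, HWL-first minus no-HWL-first: (2μ − t + d − c) − (2μ + d − t) = **−c**, so d cancels here too.

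The remark looks for a negative gap. With c = 0, any d < 0 produces one. With c > 0, d = c/2 removes it and a larger d reverses it, whatever the SD.

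**Size in SD units, c = 0.** The SD of a within-person difference is √(2 × (1 − 0.5)) = 1 SD. The SE of the gap is √(2/124) = 0.127 SD. Rejection rates for a two-sided 5% test (4,000 simulated trials per setting; normal approximation in parentheses):
- d = 0: 5.3% (5%)
- d = 0.05 SD, gap 0.1: 13% (12%)
- d = 0.1 SD, gap 0.2: 36% (35%)
- d = 0.2 SD, gap 0.4: 88% (88%)

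**Size in ppm, SD 17.6, t = 6.7.** The SE of the gap is 17.6 × 0.127 = 2.24 ppm.
- Creating an effect: with c = 0 and d = −2, the differences are 4.7 (HWL first) and 8.7 (HWL second). The gap of −4.0 would be significant in the remark's direction in 43% of trials, against a nominal 2.5% (88% to 24% for SDs of 10 to 25 ppm).
- Hiding an effect: with c = 3.35 (half the pilot effect) and d = +1.675, both differences are 5.025 and the gap is 0. At d = +2 the gap is +0.65, the wrong direction.

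**What the alternative contrasts can detect** (80% power, multiplier 1.96 + 0.84 = 2.8):
- Session-2 pre-smoking value by order, adjusted for the session-1 pre-smoking value: 2.8 × √(1 − 0.5²) × √(2/124) = 0.31 SD.
- Session totals by order: 2.8 × √(2 × 1.5) × √(2/124) = 0.62 SD. For eCO the SD of a total is 17.6 × √3 = 30.5 ppm and the SE is 3.88 ppm. Power is 41% if the whole 6.7 ppm persists (c = 6.7) and 14% for c = 3.35; 80% power would need about 327 and 1,305 per order.

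**The case against.** Most of the case on the other side concerns weight, and much of it stands.

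- **Status.** Persistence across sessions is not listed under Objectives and Hypotheses. The text is half a sentence with a parenthetical expectation, and Statistical Analysis plans no test of it. A reader might infer that the trial would report a lasting effect that does not exist. The documents do not support that; the rejection rates describe a test that nobody has planned.
- **Declared route for longer-term effects.** That is the 3-month call. It does not replace an order contrast, because every participant has by then had a labelled session and there is no unexposed arm.
- **Session change is conjectural.** Participants attend an onsite screening, are familiarised with procedures and get time to adapt. These steps may shrink d, but nothing shows that it is zero. The planned correlation of topography across sessions does not help, because a correlation is unchanged by a mean shift.
- **Overlap with the promised carry-over test.** Persistence into a later unlabelled session is carry-over, and the totals contrast is essentially a carry-over test. This is right. The remaining gap is that the test is not specified and is treated as a nuisance check, so it does not support the reading in Experimental Methods.
- **Weak remedy for smoking behaviour.** Also right. The totals contrast has low power and cannot be told apart from a label-by-session interaction. The more precise contrast answers a different question, about harm perception and intention.

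**Conclusion.** The point holds as a limited one. The by-order between-session difference equals 2d − c, so it does not identify persistence unless d = 0, and nothing in the plan estimates or removes d from it. The algebra is exact under an additive model. The sizes are illustrative: they rest on assumed values of d, on 124 per order and, in ppm, on an SD inferred from f = 0.19.

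A reader might go further and infer that session changes bias the main label comparison. They do not, because d cancels when the balanced orders are averaged. The primary hypotheses, the stated power and the comparison of the four labels are untouched. What needs correcting is a secondary remark that would mislead if it were followed.

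**What to change.** 1. Delete the parenthetical reading in C.5, Experimental Methods, and state that the by-order between-session difference will not be interpreted as a label effect.
2. For persistence in harm perception and intention to quit, compare session-2 pre-smoking values between the randomised orders, adjusted for session-1 pre-smoking values. Both orders are then measured at the same session, so d drops out. The items are already collected: "Intention and motivation to quit will be asked pre-/post-smoking", and likewise harm perception. The pre-smoking answers should be given before a labelled device is in view; the text does not say when the device is set out.
3. For puffing and eCO, state in Statistical Analysis that the carry-over test is the between-order contrast of session totals. Report it with its confidence interval, as exploratory, together with its low power and its confounding with a label-by-session interaction.

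The cost is a change of wording and a few extra models on existing data. The drawback is that persistence in smoking behaviour will be estimated imprecisely.
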